The number and percentage of tumors achieving Technical Success will be summarized and a 95% confidence interval will be estimated. Technical Success will be evaluated based on the margin achieved after the first ablation and prior to any repeat ablations within the first 7 days.

A similar summary will be provided for Technical Efficacy. This endpoint will be based on the scan obtained at Visit 3 and will count as successes patients with A0 or A1 margins in that scan and who did not have an A2 margin since the Visit 2B scan. Additionally, if a patient received a repeat ablation for correcting a margin (to go from A1 to A0) within the first 30 days, this will also count as a success. Patients with repeat ablations to correct an A2 margin from Visit 2B to Visit 3 will not count as success for Technical Efficacy. The number and percentage of tumors with A0 and A1 margins will be presented as a subcategorization within each presentation of Technical Success and Technical Efficacy, as well as a summarization for the number and reasons for repeat ablations through Visit 3.

Local tumor progression rates at 1, 3, 6, 9, 12, 18, 24, 30, and 36 months will be estimated using the Kaplan-Meier method and 95% confidence intervals will be provided. Any repeat ablation required after Visit 3 (Month 1) will be identified as an instance of local tumor progression. A similar summary will be provided for the 36-month overall and progression-free survival rates.

Confidential Page 41 of 61

The number and percentage of patients experiencing AEs will be summarized at the preferred term level using the Society of Interventional Radiology (SIR) clinical practice guidelines for event categorization. A similar summary will also be provided for device-related AEs, procedure-related AEs, all SAEs, device-related SAEs, and procedure-related SAEs. Adverse event rates will also be estimated using cumulative patient years of exposure as the denominator as well as total number of patient ablations.

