The visit in the outputs should be derived based on the above visit schedule.

If a visit is performed "out of window" (i.e.between two visit windows), the visit should be analyzed as part of the the visit closest in terms of time or number of days as outlined by visit schedule, above. More details can be found in Table 1 of the protocol.

In case any retest performed within one visit, the visit in the outputs will be derived based on the above time windows. The visit with worst result will be used as the planned visit.

5 Levels of Significance

Given that no hypotheses are formally being tested in this study, no levels of significance are specified. Estimation of specified study endpoints will be performed using two-sided 95% confidence intervals (CI).

6 Analysis Sets

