8.4.1 Effectiveness Endpoint(s)

All effectiveness endpoints will be summarized for FAS and PPS. Subjects in run-in analysis set will be also summarized for technical success and technical efficacy endpoints.

The effectiveness endpoints are defined, as follows:

Technical Success

Technical Success, defined as a combination of A0 ablations (complete tumor ablation with a surrounding 5 mm margin) and A1 ablations (complete tumor ablation with inadequate margins) based on contrast-enhanced MRI performed at Visit 2B (up to 7 days following the original ablation procedure).

The number and percentage of tumors achieving Technical Success will be summarized. Percentage will be calculated relative to the total count of evaluable target tumor lesions at Visit 2B. A 95% confidence interval will be estimated using wald method. The number and percentage of tumors with A0, A1 and A2 margins will be presented as a sub-categorization :

Note: Ablation evaluation by Investigator is collected in "Ablation Zone Assessment" CRF page. A0: complete tumor ablation with adequate margin (surrounding 5 mm margin) A1: complete tumor ablation with inadequate margins

A2: Incomplete tumor ablation

A subject archieving technical success is defined as a subject with all tumors reaching A0 or A1 at Visit 2B. The number and percentage of subjects archieving Technical Success will be summaried as well. Percentage will be calculated relative to the total number of subjects in relavent analysis population (FAS or PPS). A 95% confidence interval will be estimated using wald method.

Number and percentages of reasons for A1 and A2 ablation categorization will be also summarized.

Technical Efficacy

Technical Efficacy, defined as a combination of A0 ablations (complete tumor ablation with a surrounding 5 mm margin) and A1 ablations (complete tumor ablation with inadequate margins), based on contrast-enhanced MRI scans at Visit 3 (1 month +/- 7 days) after the original ablation procedure.

Tumor-level analysis method is same as that of primary endpoint. The number and percentage of tumors achieving Technical Efficacy will be summarized and a 95% confidence interval will be estimated using Wald method. The number and percentage of tumors with A0 and A1 margins will be presented as a sub-categorization within each presentation of Technical Efficacy, as well as a summarization for the number and reasons for repeat ablations through Visit 3.

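### SAP 8.4.1 omits the protocol's condition that Technical Success is graded before any repeat ablation, so a tumour whose only Visit 2B MRI follows a repeat is graded on the wrong ablation

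*SAP*

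**What the plan says.** Protocol 8.1, and the synopsis in the same terms: "Technical Success will be evaluated based on the margin achieved after the first ablation and prior to any repeat ablations within the first 7 days".

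SAP 8.4.1 keeps the A0-or-A1 definition and the 7-day window counted from the original procedure, but sets no condition on a repeat ablation in between. At subject level: "A subject archieving technical success is defined as a subject with all tumors reaching A0 or A1 at Visit 2B". The two denominators differ. For tumours: "Percentage will be calculated relative to the total count of evaluable target tumor lesions at Visit 2B". For subjects: "Percentage will be calculated relative to the total number of subjects in relavent analysis population (FAS or PPS").

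Three other SAP rules bear on which scan is used:

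- Section 4, on retests within a visit: "The visit with worst result will be used as the planned visit".
- Section 4, on out-of-window visits: "the visit should be analyzed as part of the the visit closest in terms of time or number of days".
- Section 8.1.4 leaves unscheduled measurements out of by-visit summaries.

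SAP 8.4.1 does have a repeat-ablation safeguard, but only under Technical Efficacy, where any A2 since the Visit 2B scan rules out success even if it was corrected.

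**The concern.** Technical Success is meant to describe what the first ablation achieved. It is the effectiveness result named for the first analysis in Protocol 8.1. The protocol's own sentence foresees repeat ablations inside the 7-day window, and its SAE definitions (14.2) provide for a hospital stay prolonged by an extra margin procedure, so early repeats were expected.

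A programmer working from the SAP alone would take the Visit 2B grade without asking whether a repeat came first. An incomplete first ablation that was re-treated before its first MRI would then count as a first-ablation success. There is no hypothesis test and no acceptance criterion (Protocol 8.4), so the estimate and its confidence interval are what readers will judge.

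**Working it through.** **Planned size.** Reproduced first because it sets the denominator. The target is 100 subjects with 1-year data and 20% dropout (Protocol 8.2.1, SAP Section 7): 100 / (1 − 0.20) = 125. Adding 4 sites × 3 run-in patients = 12 gives 137. Both figures match the plan. The point does not depend on them beyond the FAS of 125, assuming all 125 are ablated.

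**Which scan is graded under each text**

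| Scans in the Visit 2B window | Protocol 8.1 | SAP as written |
|---|---|---|
| One MRI, no earlier repeat | That MRI | That MRI: agrees |
| MRI before and MRI after a repeat | The earlier MRI | Worst result: recovers a first-ablation A2 |
| As above, but the earlier MRI was entered as unscheduled | The earlier MRI | Unclear: Section 4 would use it, 8.1.4 may drop it |
| Only an MRI after the repeat | No qualifying grade | The later grade is credited |

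The last row is the gap; the third is a smaller ambiguity. The Technical Efficacy safeguard does not help in the last row, because the first-ablation A2 was never recorded on an MRI.

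**Effect by first-ablation grade, last row.** If the first ablation was A2 and the later MRI shows A0 or A1, a failure becomes a success. If it was A1 and becomes A0, it was a success either way, so only the sub-category changes.

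**Size at subject level.** Let k be the number of such A2 subjects. The overstatement is k / 125, or 0.8 points each.

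Illustration (assumption): one tumour per subject and 11 first-ablation A2, close to the 91.6% (98/107) cited for this device in Protocol 4.2. The correct rate is 114/125 = 91.2%. The Wald interval, which is the SAP's method, is p ± 1.96 × √(p(1 − p)/n) = 86.2% to 96.2%.

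| k (assumed) | SAP-credited rate | Wald 95% CI |
|---|---|---|
| 0 | 114/125 = 91.2% | 86.2 to 96.2 |
| 1 | 115/125 = 92.0% | 87.2 to 96.8 |
| 3 | 117/125 = 93.6% | 89.3 to 97.9 |
| 5 | 119/125 = 95.2% | 91.5 to 98.9 |

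**Size at tumour level.** This depends on how the k tumours are otherwise handled. As failures, each is worth 1/125 = 0.8 points with 125 tumours, or 1/200 = 0.5 points with 200 (tumour counts assumed). As non-evaluable, k = 3 gives 114/122 = 93.4%, against 93.6% when credited. So excluding them hardly moves the tumour-level estimate, and a failure analysis is needed to show the possible range.

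**The case against.** The strongest reply is that this is an omission in a rare case. The protocol's short endpoint definitions (7.1.2, 7.1.6) lack the clause too, and the SAP says nothing against it. In the ordinary pathway the 7-day MRI is the scan that classifies the first ablation (Protocol 7.2.2), and Protocol 8.1 places A2 corrections between Visit 2B and Visit 3. Ultrasound and CT margin checks are listed as procedure-day details (7.2.4), and several ablation sessions may belong to one procedure (7.2.3). No passage describes a separate procedure a few days later without an MRI first. All of this stands, and it makes the case narrow. It does not restore the missing rule.

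It is also said that re-ablated cases stay visible, because results are split by initial-only and repeat ablation (SAP 8.9). That helps in part. The repeat group pools every repeat in the first 30 days and does not separate those before the first MRI.

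A reader might infer more than the documents support:

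- **That a late first MRI, around days 8 to 15, would be read as Visit 2B.** Day 15 is the midpoint of the window edges, (7 + 23)/2. The endpoint's own 7-day limit can equally be read to exclude such a scan.
- **That the bias is known to be material.** No source gives k. Cited rates of about 91% to 97% are no yardstick, since they mix different endpoints, and the 97.1% in Protocol 4.1.1 does not match its own count (1276/1363 = 93.6%).
- **That a tumour re-ablated before any MRI has failed.** Protocol 8.1 does not say so. Counting it as a failure in the main tumour-level analysis would impute an outcome, against the observed-data rule in Protocol 8.6, and would penalise a first-ablation A1.

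**Conclusion.** The point holds in a limited form. The SAP drops a stated analysis rule, and no other SAP section restores it. Where a tumour's only Visit 2B MRI follows a separate repeat ablation, the SAP credits a grade that Protocol 8.1 excludes. Inflation requires a first-ablation A2 and a later A0 or A1, and is then 0.8 points per subject in an FAS of 125. The frequency is unknown, so the illustrated totals show scale and do not predict the result. Only estimation is affected, because nothing is tested.

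It would be too strong to say that the SAP redefines Technical Success in general, or that margin corrections from A1 to A0 raise the rate. The two texts agree in the ordinary pathway, and A1 is already a success.

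**What to change.** Amend SAP 8.4.1, Technical Success, at tumour and subject level:

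- Restore the Protocol 8.1 condition. Take the grade from a contrast-enhanced MRI done after the original ablation procedure and before any separate repeat procedure on that tumour.
- Include a pre-repeat MRI that lies in the Visit 2B window even if it was entered as unscheduled.
- Bar any post-repeat scan from being mapped to Visit 2B for this endpoint.
- State that a tumour with no pre-repeat MRI has no Technical Success grade. At tumour level it is non-evaluable, with a sensitivity analysis counting it as a failure. At subject level the subject is not a success, which follows from the full FAS or PPS denominator already in the SAP.
- Report the number of such tumours.

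The cost is SAP wording and a comparison of MRI dates with repeat-ablation dates. SAP 8.1.5 already lists scan and ablation dates among the available data. Sample size and data collection do not change. The reported rate may be slightly less favourable, partly because a subject whose first ablation was A1 but who was re-ablated before any MRI would also not count as a success.

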A subject archieving technical efficacy is defined as a patient with all tumors reaching A0 or A1 at Visit 3. The number and percentage of subjects archieving Technical Efficacy will be summaried as well. Percentage will be calculated relative to the total number of subjects in relavent analysis population (FAS or PPS). A 95% confidence interval will be estimated using wald method. But the subjects who have any A2 margin since the visit 2B scan would not be counted as technical efficacy regardless if the tumor was corrected with repeat ablation.

Local tumor progression (LTP) (the 2nd interim, final)

LTP is evaluated after the ablation of the target tumor(s). LTP describes the appearance of tumor foci at the edge of the ablation zone, after at least one contrast-enhanced follow-up

MRI scan has documented adequate ablation, and an absence of viable tissue in the target tumor and surrounding ablation margin, by using imaging criteria.

Tumor-level analysis method is same as that of Technical Success endpoint. The number and percentage of tumors with LTP will be summarized and a 95% confidence interval will be estimated using Wald method.

A subject with LTP is defined as a patient with any target tumor LTP. The number and percentage of subjects with LTP. Percentage will be calculated relative to the total number of subjects in relevant analysis population (FAS or PPS).

Subgroup analysis is defined in SAP section 8.11. Two subgroup columns (subjects/tumors with only initial ablation and subjects/tumors with repeat ablation) and 1 total column will be used as analysis columns in LTP tables.

Tumor type (primary HCC and recurrent HCC and other) will be another subgroup variable for LTP (analyzed for patient level and tumor level).

LTP start date is the date of initial ablation of a subject. The event date of LTP is collected in "Ablation Zone Assessment" CRF page as following table:

		Event/Censoring	
	Situation	Date	Outcome
No post-base	eline or no baseline Ablation Zone A	ssessment	
	No post-baseline local tumor	Date of initial	
A1	evaluation	ablation	Censored
	No baseline local tumor	Date of initial	
A2	evaluation	ablation	Censored
With baselin	e and post-baseline tumor assessm	ents	
	Local Tumor Progression and zero or one missed tumor assessment prior to confirmed		
B1	LTP	Date of first LTP date	Event

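### SAP 8.4.1 states the A2 exclusion for Technical Efficacy for subjects only, so as written an A2 tumour corrected before Visit 3 counts as a tumour-level success

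*SAP*

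**What the plan says.** **SAP 8.4.1, Technical Efficacy, tumour level.** The endpoint is A0 plus A1 on the Visit 3 scan, reported as a number and percentage of tumours with a Wald 95% confidence interval. No condition is put on earlier grades. For the method the text says "Tumor-level analysis method is same as that of primary endpoint", but neither document designates a primary endpoint. The parallel sentence for local tumour progression reads "Tumor-level analysis method is same as that of Technical Success endpoint", which suggests that Technical Success is meant. The Technical Success method is a Visit 2B count ("Percentage will be calculated relative to the total count of evaluable target tumor lesions at Visit 2B") and has no rule for a tumour re-treated between scans.

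**SAP 8.4.1, Technical Efficacy, subject level.** A subject succeeds if all tumours are A0 or A1 at Visit 3. Then follows the exclusion: "But the subjects who have any A2 margin since the visit 2B scan would not be counted as technical efficacy". The end of that sentence makes the exclusion hold "regardless if the tumor was corrected with repeat ablation".

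**Protocol 8.1.** Technical Efficacy is introduced as a summary like the one for Technical Success, which counts tumours. The rule is then worded for patients: the endpoint will "count as successes patients with A0 or A1 margins in that scan and who did not have an A2 margin" since Visit 2B. It continues: "Patients with repeat ablations to correct an A2 margin from Visit 2B to Visit 3 will not count as success for Technical Efficacy". A1 margins are treated differently: a "repeat ablation for correcting a margin (to go from A1 to A0) within the first 30 days, this will also count as a success".

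**The concern.** Protocol 8.1 puts a patient-worded exclusion inside a tumour-count summary. The SAP splits the endpoint into two levels and carries the exclusion to only one of them. A programmer who follows the SAP alone would count a corrected A2 tumour as a success. One who also works from Protocol 8.1 might exclude it. The two would report different tumour-level rates from the same data.

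Under the first reading, the tumour-level and subject-level results can contradict each other for the same patient. Technical Efficacy is also a readout of the first interim analysis (SAP 8.6), and its tumour-level rate feeds the tumour-type and site forest plots (SAP 8.9 and 8.10). Protocol 8.4 sets no acceptance threshold and judges performance on all the data in the context of other therapies. The estimates and their intervals therefore carry the evidence.

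**Working it through.** **1. The plan's own size.** Protocol 8.2.1 asks for at least 100 patients with data to one year and allows 20% dropout: 100 / (1 − 0.20) = 125. The run-in adds 3 × 4 = 12, giving 137. This reproduces the stated total, and nothing below changes it.

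**2. The rules applied to a patient with one target tumour.**

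| Visit 2B | Between scans | Visit 3 | SAP, tumour level | SAP, subject level | Protocol 8.1 |
|---|---|---|---|---|---|
| A0 or A1 | nothing | A0 or A1 | success | success | success |
| A1 | re-ablated within 30 days | A0 | success | success | success |
| A2 | nothing | A2 | failure | failure | failure |
| A2 | re-ablated | A0 or A1 | **success** | failure | failure |

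Where the tumour is re-treated, the rules disagree only in the last row. Protocol 8.1 names that situation, so it can arise.

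**3. Whether another SAP rule closes the gap.** SAP section 4 keeps the worst result when a test is repeated within one visit. Visit 2B and Visit 3 are separate visits, so that rule does not carry the A2 grade forward.

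**4. Effect per tumour.** With *k* corrected A2 tumours among *T* evaluable tumours, the rise in the rate is *k*/*T*. The documents give neither number. Two assumed values of *T*:

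- One tumour per patient: *T* = 125, and 1/125 = 0.8 points each.
- The tumours-per-patient ratio of the Chinese multicentre series in Protocol 4.1.1: 1363/1007 = 1.354, *T* = 125 × 1.354 ≈ 169, and 1/169 = 0.6 points each.

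| *k* (assumed) | *T* = 125 | *T* = 169 |
|---|---|---|
| 0 | 0 | 0 |
| 2 | 1.6 points | 1.2 points |
| 5 | 4.0 points | 3.0 points |

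**5. Illustration from the protocol's cited 221-patient series (Protocol 4.1.1).** It reports 201 patients with initial complete ablation and 8 more counted under secondary technique effectiveness. With the Wald interval p ± 1.96 √(p(1 − p)/n):

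- Corrected cases as failures: 201/221 = 90.95% (87.17 to 94.73).
- Corrected cases as successes: 209/221 = 94.57% (91.58 to 97.56).
- Difference: 8/221 = 3.62 points, or about 4.5 tumours if *T* = 125.

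These are patient-level figures with technique effectiveness assessed at one month, so they do not estimate how many tumours in this trial would be A2 at Visit 2B.

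**The case against.** The strongest reply is that the protocol already answers the question. Its paragraph starts from a tumour count and gives the A2 exclusion as part of what the endpoint means. The SAP's exclusion closes the Technical Efficacy block and mentions the tumour being corrected. This makes exclusion the likely intent, and that part stands. It does not settle the tumour-level rule. The SAP sentence is about subjects, and a patient-worded rule leaves open whether only the A2 tumour fails or all of that patient's tumours fail.

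The second reply is that the effect would be visible and decides nothing. The study has no hypothesis test or threshold. A2 tumours are tabulated at Visit 2B, as are the number of and reasons for repeat ablations through Visit 3. With similar denominators, a tumour-level Technical Efficacy rate above the Technical Success rate would be a warning sign. This limits the seriousness, but it does not correct the rate or its interval.

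A reader might also infer from the borrowed method that Technical Efficacy would be divided by tumours evaluable at Visit 2B. That is over-literal. The endpoint is tied to Visit 3, and the same shorthand is used for local tumour progression, which is not a Visit 2B endpoint. Naming the denominator is sensible tidying, not the point itself.

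**Conclusion.** The point holds in a limited form. Followed as written, SAP 8.4.1 counts a corrected A2 tumour as a tumour-level success, against Protocol 8.1 and against the SAP's own result for the same subject. The subject-level rule is clear and agrees with the protocol. No hypothesis, sample size or decision rule is touched.

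The size is *k*/*T*: 0.8 points per tumour at an assumed 125 tumours, and about 3.6 points if the 221-patient series applied, which is also an assumption. It is zero if no A2 tumour is corrected before the Visit 3 scan.

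Three stronger readings are tempting and are not supported:

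- *The sponsor intends to count these tumours, or the reported rate will be inflated.* The documents show an unstated rule, and the protocol points the other way.
- *The inflation could be as large as the whole A2 rate.* That needs a Visit 2B A2 rate and correction of every A2 tumour. Neither is documented.
- *All of the rise must fall in the repeat-ablation column.* SAP 8.9 defines that group by repeats in the first 30 days, while the Visit 3 window runs 7 days beyond one month. A repeat after day 30 but before a late scan would fall in neither subgroup.

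**What to change.** Edit SAP 8.4.1 as follows.

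- In the tumour-level sentence, replace the reference to a primary endpoint with Technical Success.
- Add: *A tumour achieves Technical Efficacy if it is A0 or A1 at Visit 3 and was not A2 on any scan from Visit 2B to Visit 3, whether or not it was corrected by repeat ablation; a tumour re-ablated from A1 to A0 within 30 days remains a success. The denominator is target tumours evaluable at Visit 3 plus any tumour graded A2 from Visit 2B onward, which counts as a failure even without a Visit 3 scan.*
- Add a separate non-success row to the table for A2 tumours corrected by repeat ablation.
- Have the sponsor confirm that only the A2 tumour fails, not the patient's other tumours. The proposed wording assumes this, because the protocol's rule is written for patients.

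The second half of the denominator sentence is needed. A denominator of Visit 3-evaluable tumours alone would drop a known A2 failure that has no Visit 3 scan, while its subject stays in the analysis set as a failure.

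The cost is a few SAP sentences and one table row, using grades already collected. Protocol 8.7 allows analysis changes to be made in an amended SAP, so no protocol amendment is required. The downside is a slightly less favourable tumour-level rate.

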8.3. Expected Dropout Rate

The expected dropout rate in this study is 20%.

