	Local Tumor Progression and over one missed tumor assessment prior to confirmed	Date of the latest evaluable local tumor assessment prior to the missed	
B2	LTP	assessment	Event
		Date of last local	
		tumor assessment	
	No progression, either alive or	with no documented	
С	death	LTP	Censored

Table 3: Censoring Rules for LTP

		Date of last tumor assessment with no documented	
D	Dead	progression	Censored
		Date of last tumor	
		assessment with no	
		documented	
E	Withdrawal by Subject	progression	Censored

Local tumor progression rates at 3, 6, 9, 12, 18, 24, 30, and 36 months will be estimated using the Kaplan-Meier (K-M) method and 95% confidence intervals (Greenwood's formula) will be provided.

The K-M curve of time to LTP will be provided.

Secondary efficacy rate (the 2nd interim, final)

Secondary efficacy rate is defined as the percentage of subjects whose tumors have undergone successful repeat ablation following identification of local tumor progression at any time during study follow up.

It could be found in CRF page, Ablation Zone Assessment, "Re-ablate with Neuwave". For subgroup that has LTP and used Certus to re-ablate, the number and percentage of subjects achieving secondary efficacy, will be summarized and a 95% confidence interval will be estimated using wald method.

Progression-free survival (PFS) (the 2nd interim, final)

PFS is defined as length of time from initial ablation until disease progression.

Table	e 4. Censoring Rules for PFS		
	Situation	Event Date	Outcome
No po	st-baseline or no baseline Ablation Zo	ne Assessment	
	No post-baseline tumor evaluation		
A1	and alive	Date Ablation performed	Censored
	No post-baseline tumor evaluation		
	but died on or before the second		
A2	scheduled tumor assessment	Date Ablation performed	Censored
With baseline and post-baseline tumor assessments			

Table 4: Censoring Rules for PFS

В	Any Tumor Progression and zero or one missed tumor assessment prior to progression	Date of first progression	Event
		Date of last progression	
	PD happens after >=2 consecutively	assessment before	
С	missing tumor assessment	missing assessments	Censored
		Date of last progression	
		assessment with no	
D	No progression	documented progression	Censored

Progression-Free Survival rate will be estimated using the Kaplan-Meier method and 95% confidence intervals (Greenwood's formula) will be provided for 6, 12, 18, 24, 30, 36 months.

The K-M curve of time to progression will be provided.

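### The SAP's added crude LTP percentages count subjects and lesions lost to follow-up as LTP-free; the effect is modest, and matters most at tumour level, where no time-to-event estimate is stated

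*SAP*

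**What the plan says.** Protocol 8.1 describes one way of estimating LTP rates: at visits from 1 to 36 months they "will be estimated using the Kaplan-Meier method and 95% confidence intervals will be provided". SAP 8.4.1 keeps this ("Local tumor progression rates at 3, 6, 9, 12, 18, 24, 30, and 36 months will be estimated using the Kaplan-Meier (K-M) method"), with Greenwood intervals and a curve. Its Table 3 gives the censoring rules. A subject with no post-baseline evaluation is censored on the day of initial ablation. Subjects who die or withdraw are censored at the last assessment without progression.

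The same SAP section adds two crude summaries that the protocol does not describe.

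- Subject level: "A subject with LTP is defined as a patient with any target tumor LTP", and "Percentage will be calculated relative to the total number of subjects in relevant analysis population (FAS or PPS").
- Tumour level: "The number and percentage of tumors with LTP will be summarized", with a Wald 95% interval. For the denominator, "Tumor-level analysis method is same as that of Technical Success endpoint", and there "Percentage will be calculated relative to the total count of evaluable target tumor lesions at Visit 2B".

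The LTP text also asks for columns by initial-only versus repeat ablation in the LTP tables, and for tumour type as a further subgroup at patient and tumour level. SAP 8.9 says subgroup results will be shown as a percentage with a 95% interval in a forest plot. Protocol 8.3 says "The expected dropout rate in this study is 20" percent. Protocol 8.6 and SAP 8.7 allow no imputation.

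**The concern.** LTP is looked for on scans over 36 months. A percentage that divides by a number fixed at the start gives full LTP-free credit to anyone who leaves before progression could be seen. A subject never scanned after ablation contributes nothing to the Kaplan-Meier estimate (censored at day 0) but is a complete non-event in the crude percentage. That sits badly with the protocol's rule that only observed data are analysed. It also departs from the SAP's general convention (8.1.8) that missing observations are left out of denominators unless otherwise stated; the subject-level LTP sentence states otherwise.

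The crude figure also has no time point. SAP 8.1.6 takes in all data up to the cut-off, and recruitment is planned over about 8 months, so the analysis at 12 months would mix follow-up of about 12 to 20 months (12 + 8).

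The trial has no hypothesis or acceptance criterion. Protocol 8.4 judges performance from all the data in the context of other therapies, so the estimates are the result. Two LTP rates on different footings, with the crude one lower, leave room to cite the more favourable one. At tumour level the crude figure is the only one stated.

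**Working it through.** **The plan's own figure.** 100 subjects with one-year data and 20% dropout: 100 / (1 − 0.20) = 125. Adding 3 × 4 = 12 run-in patients gives 137. Both reproduce. The 20% is tied there to one-year data; the documents do not say how much dropout is expected by month 36, or whether the 20% includes deaths.

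**Inputs for sizing the effect.**
- 3-year overall survival 72.5%, from the Chinese multicentre series cited in Protocol 4.1.1.
- Net 36-month LTP risk 12% (assumed). The same series gives 5.9% at a mean of 17.3 months; at a constant hazard, 1 − (1 − 0.059)^(36/17.3) = 11.9%.
- Dropout 20% over 36 months, exclusive of deaths; alternatively 20% per year.
- Constant, independent hazards for LTP, death and dropout (assumed).

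**Cumulative hazards over 36 months.** L = −ln(0.88) = 0.1278; D = −ln(0.725) = 0.3216; W = −ln(0.80) = 0.2231, or 3 × 0.2231 = 0.6694 at 20% per year.

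**Three quantities.**
1. Net risk, which Kaplan-Meier with deaths censored estimates: 1 − exp(−L) = 12.0%.
2. Cumulative incidence with death competing and no dropout: L/(L+D) × [1 − exp(−(L+D))] = 0.1278/0.4494 × (1 − 0.88 × 0.725) = 0.2844 × 0.3620 = 10.3%.
3. Crude percentage: L/(L+D+W) × [1 − exp(−(L+D+W))] = 0.1278/0.6726 × (1 − 0.88 × 0.725 × 0.80) = 0.1901 × 0.4896 = 9.3%. At 20% dropout per year: 0.1278/1.1188 × (1 − 0.88 × 0.725 × 0.512) = 0.1143 × 0.6733 = 7.7%.

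**Splitting the gap from 12.0% to 9.3%.** 12.0 − 10.3 = 1.7 points come from the treatment of deaths, and 10.3 − 9.3 = 1.0 point comes from dropout. With 125 subjects, the 1.0 point is about one LTP case.

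| Scenario | Net (1 − KM) | Cumulative incidence | Crude | Crude vs cumulative incidence |
|---|---|---|---|---|
| 36 months, net LTP 12%, 20% dropout by month 36 | 12.0% | 10.3% | 9.3% | about −10% |
| 36 months, net LTP 12%, 20% dropout per year | 12.0% | 10.3% | 7.7% | about −25% |
| 36 months, net LTP 20%, 20% dropout by month 36 | 20.0% | 17.2% | 15.6% | about −10% |
| 36 months, net LTP 20%, 20% dropout per year | 20.0% | 17.2% | 12.9% | about −25% |
| 12 months, cited LTP hazard and 1-year survival 91.2%, 20% dropout by month 12 | 4.1% | 4.0% | 3.6% | about −10% |

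A simulation on the actual visit schedule, using the cited LTP hazard and 20% dropout by month 36, gave the same order: crude 8.9%, cumulative incidence 10.1%, 1 − KM 11.9%.

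**Extreme case.** If 25 of 125 subjects were never assessed after ablation, the crude rate would be 100/125 = 0.80 of the rate in those assessed, for example 8% instead of 10%.

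**Tumour level.** The same mechanism applies from Visit 2B onward. The documents do not give the expected number of lesions per patient, so no separate figure is computed. The Wald interval also treats up to three lesions in one patient as independent.

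**The case against.** The strongest reply is that the LTP rates named in the protocol are the Kaplan-Meier rates. The SAP plans them at eight time points with censoring of deaths, withdrawals and unassessed subjects. The crude percentage is an extra descriptive line in a trial where everything is descriptive. At subject level this stands: a reader might infer that the trial's LTP result as a whole is biased in the device's favour, and the documents do not support that.

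Four other strong readings also fail.
- That both crude percentages divide by everyone in the analysis set. Only the subject-level one does; the tumour-level one uses lesions evaluable at Visit 2B.
- That deaths are wrongly counted as LTP-free. A patient scanned until death without LTP did not have LTP and is a proper non-event for a cumulative incidence. Only LTP arising between the last scan and death is missed. Kaplan-Meier that censors deaths overstates the proportion who actually develop LTP.
- That the subgroup tables receive only the crude figure. The ablation columns are specified for LTP tables without excluding Kaplan-Meier, and Protocol 8.1 asks for all efficacy endpoints in those two groups. The SAP is unclear for tumour type, not restrictive.
- That a per-subject time origin rules out a tumour-level Kaplan-Meier. It does not; the SAP simply states none.

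It can also be said that 1 point is small beside a Wald half-width of about 5 points (1.96 × √(0.10 × 0.90/125) = 5.3 points), and that the cited Chinese series reports LTP as a crude tumour proportion (78/1363), so the crude format helps comparison. Both are fair. The first makes the effect modest, but it pushes consistently in one direction. The second is a reason to keep the count with a clear label.

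**Conclusion.** The point holds in limited form. Followed as written, the crude LTP percentages give lost subjects and lesions LTP-free credit, while Table 3 censors such subjects. The overall subject-level Kaplan-Meier rate is not affected. The consequence is greatest at tumour level, where the crude percentage is the only stated estimate, and next for tumour type, where no time-to-event estimate is clearly stated.

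Dropout lowers the crude figure by about 10% relative (10.3% to 9.3%) with 20% dropout over 36 months, and by about 25% (10.3% to 7.7%) with 20% per year. The whole gap from 12% to 9.3% should not be read as bias: 1.7 of the 2.7 points is the difference between a net risk and a cumulative incidence.

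These figures rest on constant independent hazards, on survival borrowed from a background study, on an assumed 12% LTP risk, and on the 20% being exclusive of deaths. The documents list death among the reasons for leaving the study and do not settle this last point. If the 20% includes deaths, the dropout effect is smaller.

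**What to change.** In SAP 8.4.1:

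- Drop the Wald interval for LTP. Keep the crude figure only under a label such as 'observed events, not adjusted for follow-up', and show beside it the numbers assessed, lost and dead.
- Make the time-to-event estimate at the stated months the reported LTP rate at subject level, at tumour level with a variance clustered on subject, and in each subgroup column, including tumour type.
- Use the planned Kaplan-Meier estimate and add a cumulative incidence with death as a competing event, so that the two treatments of death can be told apart.

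The cost is SAP wording, table shells and a little more analysis. The tumour-level and subgroup LTP rates will come out slightly less favourable. The protocol-specified overall Kaplan-Meier rate does not change.
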